#### Serious adverse event or serious adverse drug reaction

An adverse event or adverse drug reaction that is:

- fatal;
- life-threatening;
- requires or prolongs inpatient treatment;
- results in persistent or significant disability or incapacity; or
- is a congenital anomaly or birth defect.

Note:

- the term 'life-threatening' in the definition of 'serious' refers to an event or reaction in which the patient was at risk of death at the time of the event; it does not refer to an event or reaction which hypothetically might have caused death had it been more severe; and
- in accordance with the ICH Guideline on Clinical Safety Data Management: Definitions and Standards of Expedited Reporting, events or reactions that are not immediately life-threatening or may not result in death or hospitalisation, but might jeopardise the subject or require intervention to prevent one of the other outcomes listed above, should usually be considered serious.

#### Significant adverse event or reaction

An adverse event or reaction which is not serious, but is otherwise significant. The following will be considered significant:

- a marked haematological or other laboratory abnormality;
- an adverse event or reaction that leads to an intervention, including withdrawal of drug treatment, dose reduction or significant additional concomitant therapy; or
- any adverse event or reaction that the investigator considers to be significant.

#### 16.2 **Procedures for recording adverse events**

Subjects will be carefully monitored for adverse events. The investigator or delegate will question the subjects about adverse events using a non-leading question, such as 'How are you feeling?' The investigator will also record adverse events reported spontaneously by the subjects. Clinically significant changes in the findings of physical examination, and clinically significant abnormalities in the results of objective tests (eg laboratory variables, x-ray, ECG) may also be recorded as adverse events. The investigator will use the following criteria when deciding whether to report an abnormal result as an adverse event.

- 1. The test result is associated with accompanying symptoms.
- 2. Results of additional diagnostic tests cause concern or necessitate medical intervention.
- 3. As a consequence of the test result, the dose administered to the subject is changed, the subject is withdrawn, or the subject is given concomitant treatment.
- 4. The investigator considers the result to constitute an adverse event.

If any of the above criteria are met, the investigator will report the result as an adverse event.

A record will be kept in the CRF of all adverse events as reported, whether believed to be related or unrelated to the treatment. The record will include the following.

- Clinical symptoms: a simple, brief description.
- Date and time of onset and end of clinical symptoms.
- Frequency: constant or intermittent.
- Severity. The following categories will be used:

*Mild:* the adverse event does not interfere with the volunteer's daily routine, and does not require intervention; it causes slight discomfort.

*Moderate:* the adverse event interferes with some aspects of the volunteer's routine, or requires intervention, but is not damaging to health; it causes moderate discomfort.

*Severe:* the adverse event results in alteration, discomfort or disability which is clearly damaging to health.

• Relationship to treatment: The assessment of relationship of adverse events to the administration of IMP is a clinical decision based on all available information at the time of the completion of the case report form. The following categories will be used.

### Possibly related

An event for which, after careful medical evaluation, a connection with trial medication cannot be ruled out with certainty. The event occurs after exposure to the test product. The event may occur at a reasonable time in relation to the time of administration of the IMP, but might also be attributable to a commonly occurring alternative cause. Alternatively, the event may not occur at a reasonable time in relation to the time of administration of the IMP, but might also be attributable to a commonly occurring alternative cause.

#### Unlikely to be related

An event which occurs before exposure to the test product, or which does not occur at a reasonable time in relation to the time of administration of the IMP, and can be attributed to the patient's condition or a commonly occurring alternative cause. Alternatively, the event is unrelated to the trial, eg road traffic accident, unless it can be demonstrated that the treatment could have caused the event.

- Action taken: none, drug treatment, subject withdrawn, other (specified).
- Outcome: cleared, still present, or not known.

### 16.3 **Procedures for dealing with serious adverse events**

In the event of any serious adverse event which, in the investigator's opinion, justifies termination or modification of the trial, dosing will be stopped and the sponsor will be informed immediately (within 24 h of the investigator becoming aware of the event) by telephone or facsimile, as follows.

Telephone:	0800 h–1800 h:	[name]
	1800 h–0800 h:	[name] or [name]
Fax:	(24 hours):	[name]

For all serious adverse events, the investigator will complete a serious adverse event form and provide it to the sponsor and the chief investigator, either directly or by facsimile, within 24 h of his becoming aware of the event. The chief investigator will notify the main research ethics committee (REC) of serious adverse events that occur during this trial, if applicable, in accordance with the standard operating procedures issued by NRES.

The sponsor will notify the Medicines and Healthcare products Regulatory Agency (MHRA) of all suspected unexpected serious adverse reactions (SUSARs), and will be responsible for ensuring that the main REC is notified of SUSARs, if applicable. SUSARs that are fatal or life-threatening must be notified to the MHRA and REC within 7 days after the sponsor has learned of them. Other SUSARs must be reported to the REC and MHRA within 15 days after the sponsor has learned of them.

# 16.4 Procedures for handling withdrawals due to adverse events

The investigator will assess the reason for withdrawal as far as possible and will fully record the circumstances and medical details. Provided that subjects give written informed consent, they will undergo the standard medical examination and laboratory tests at withdrawal from the trial which they would have undergone had they completed it (see also Section 10.4).

# 17 Data management and quality assurance

The data will be securely stored by the investigator. After the CRFs have been signed off by the principal investigator, the original NCR copies will be sent to the Data Management department at HMR, where they will be securely stored.

Data will be double-entered into a clinical database management system (ClinPlus Version 3.3), which is based on SAS® Version 9.2. Edit checks and generation of queries will be done in ClinPlus. Tabulations and listings will be produced using validated, trial-specific SAS® programs.

Any laboratory value outside the normal range will be flagged with an 'H' if it is higher than the normal range, and with an 'L' if it is lower. If, during the course of a trial, the variable changes by more than a predetermined amount, that value will receive a flag 'I' if increased, or 'D' if decreased. Therefore, if during the course of the trial a value falls outside the normal laboratory range and alters by more than the predetermined amount, it will attract a double flag. Note that the predetermined change refers to a change from baseline ('screening') measurements.

Any laboratory variable that receives a double flag will be listed separately, along with the associated variables. For example, if the serum creatinine were abnormal, then urea and electrolytes will also be listed. All double-flagged variables will be listed in the investigator's report together with a comment or explanation.

Adverse events will be coded using the version of the Medical Dictionary for Regulatory Activities (MedDRA) that is current when the database is locked.

Data will be checked by the HMR Quality Assurance (QA) Department. In addition, the HMR QA Department will audit the trial report; that audit will include checks to ensure that statistical output is correctly reproduced in the report.

# 18 Statistical methods

## 18.1 Statistical analyses

Statistical analysis will be done by HMR. A Statistical Analysis Plan will be prepared by the HMR Statistics and Data Management Department after completion of the final protocol. The statistical software package SAS® (SAS Institute, Cary, NC), version 9.2, will be used for all summaries and analyses.

### Efficacy data

The objective of this pilot study is to estimate the therapeutic response rate in the patients who receive YF476. The primary endpoint of the clinical response is defined as a 25% reduction in the size or number of endoscopically evident type I gastric carcinoids or a reduction of 25% in the gastric ECL cell density. Secondary endpoints include safety and changes in levels of biochemical markers (eg gastrin, CgA), histologic grade and quantitative PCR for ECL cell-specific products.

All variables will be summarised by descriptive statistics as appropriate. The mean or median of the following variables will be expressed as a percentage change of the mean or median response (as appropriate) compared to the baseline period: number of CgA ir-cells per unit area of mucosa CgAmuc and volume density of CgA ir-cells  $\rho_{CgA}$ ,

The data during the treatment period will be compared with baseline using ANOVA, with visit as fixed effect and subject as random effect. If insufficient data are available, the treatment comparison using ANOVA will not be done. Variables and parameters will be transformed before analysis, as appropriate.

Data from all subjects who complete the study without major protocol deviations will be included in the analysis of efficacy. The primary aim of the trial is to find out if YF476 can cause regression of gastric carcinoid tumours.

Interobserver variability will be reported to both endoscopic and histologic interpretations. A blinded endoscopist, who is unaware of the patient history, dose of YF476, or timing of the endoscopic examination, will review a random sample of endoscopic images to report the size of endoscopic lesions. In addition, a blinded pathologist, who is unaware of the patient history, dose of YF476, or timing of biopsy specimen, will review a random sample of histologic images to report the histologic grade and ECL cell density of the biopsy sample. Kappa statistics will be calculated to report the degree of agreement between the study and blinded endoscopists and between the study and blinded pathologists.

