#### 10.4 Withdrawal of subjects from the trial

Subjects are free to withdraw from the trial at any time without giving reasons. Furthermore, the investigator may withdraw a subject for medical reasons such as intolerance to trial medication, intercurrent illness, need for medication which is contraindicated, lack of efficacy of trial medication, or withdrawal of consent. The investigator will assess reasons for withdrawal as far as possible and will fully record the circumstances and medical details.

Subjects will be informed before they agree to take part in the trial that, if they withdraw:

- the investigator will stop collecting information about them; and
- they can ask the investigator to destroy any identifiable samples taken from them.

The investigator will ask withdrawn subjects to return unused trial medication, and to consent to a follow-up examination, to check that they have come to no harm as a result of taking part in the trial. Provided that subjects agree, they will undergo, at withdrawal from the trial, the standard medical examination and laboratory tests which they would have undergone had they completed the treatment regimen. The investigator will record in the CRF the results of the follow up examination of withdrawn subjects, if they give their consent for that.

For the extended treatment period, the following criteria apply:

Patients will be withdrawn from the study if they:

- have ALT or AST values >3 times the upper limit of normal;
- are found to have a prolonged QTc value (QTc ≥ 500 ms or QT prolongation with an increase of QTc > 60 ms compared to baseline);
- show any evidence of suspected drug-drug interaction; or
- experience an SAE or SUSAR which can reasonably be attributed to YF476.

If one of the criteria above is met in 2 or more subjects, dosing will be stopped in all subjects.

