#### **11.4 Previous and concomitant treatment**

Information on co-administered medicines is provided in Appendix 1. The investigator will include information about co-administered medicines in the letter to the patient's general practitioner.

Subjects must record all concomitant treatments in the diary card. Concomitant treatments will be reported in the case report form (CRF) along with their daily dosage, duration and reasons for administration. Subjects who have received any concomitant treatment may be withdrawn from the trial at the discretion of the investigator.

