# Safety data

Data from all subjects who received any trial treatment will be included in the analysis of safety.

Numerical data will be summarised using means or medians, and other descriptive statistics, according to the type and distribution of the data. Adverse events (see Section 16) will be listed and relationship to treatment assessed.

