# 18.2 Determination of sample size

The trial is an exploratory, open, pilot trial, so a power calculation is inappropriate. Gastric carcinoids are a rare condition, so the protocol sets a limit of up to 10 patients.

The results will be reviewed regularly, and if the results are unfavourable, the study will be stopped. If the results are favourable, the sponsor will set up a larger trial, probably double-blind, randomised, and placebo-controlled in design, and with a fixed dose of YF476.

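### Section 18.1 targets the response rate in treated patients but analyses only completers, so a patient withdrawn for lack of efficacy drops out of the denominator instead of counting as a failure

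*Protocol*

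**What the plan says.** Under Efficacy data, Section 18.1 of the protocol states the aim: "The objective of this pilot study is to estimate the therapeutic response rate in the patients who receive YF476". Response is defined in the same paragraph: "The primary endpoint of the clinical response is defined as a 25% reduction in the size or number of endoscopically evident type I gastric carcinoids". Alternatively, a fall of the same proportion in gastric ECL cell density qualifies. The section then names who is analysed: "Data from all subjects who complete the study without major protocol deviations will be included in the analysis of efficacy".

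Under Safety data the set is wider: "Data from all subjects who received any trial treatment will be included in the analysis of safety".

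Section 10.4 lists grounds on which the investigator may withdraw a patient, among them "lack of efficacy of trial medication". It also records what patients are told about withdrawal: "the investigator will stop collecting information about them". If they agree, withdrawn patients have a medical examination and laboratory tests; gastroscopy is not mentioned. Section 11.4 adds a discretionary ground: "Subjects who have received any concomitant treatment may be withdrawn from the trial at the discretion of the investigator".

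Section 18.2 caps the trial at 10 patients, without a power calculation, and says what follows a good result: "If the results are favourable, the sponsor will set up a larger trial".

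**The concern.** The target population and the analysis set in Section 18.1 differ. The aim concerns everyone who receives the drug; the analysis keeps only those who finish without a major deviation. No other section names an all-treated efficacy set or says how a withdrawn patient is to be classed.

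The gap matters because leaving the set can depend on the outcome. A patient withdrawn because YF476 is not working is a failure of treatment, but is removed instead of being counted as one. Withdrawal after concomitant treatment rests on the investigator's judgement in an open-label trial, so that decision too is made with the patient's course known.

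The response rate is the stated objective, and favourable results lead to a larger trial. With at most 10 patients, each exclusion shifts the rate by several percentage points. Nor can the loss usually be repaired afterwards: the primary endpoint needs gastroscopy or biopsy, and the check offered at withdrawal includes neither.

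This is not a detail left open for the SAP. The protocol itself states the set, and an SAP that follows the protocol would carry it over.

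**Working it through.** The protocol gives no figure to reproduce: there is no assumed response rate, withdrawal rate, alpha or power. The counts below are therefore assumptions, chosen to show the size of the effect.

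**Inputs**
- Patients treated: N = 10, the cap in Section 18.2.
- Responders among those treated: R = 5 or R = 3 (assumed).
- Non-responders withdrawn: w = 0, 1, 2 or 3 (assumed).

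**Formulas**
- All treated, with withdrawal without a documented response counted as non-response: R / 10.
- Completers, when the withdrawn patients are non-responders: R / (10 − w), which is the all-treated rate multiplied by 10 / (10 − w). The relative inflation is 11%, 25% and 43% for w = 1, 2 and 3.
- Intervals are exact (Clopper-Pearson) 95%.

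**Non-responders withdrawn**

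| R | w | All treated | Completers | 95% interval, completers |
|---|---|---|---|---|
| 5 | 0 | 5/10 = 50.0% | 5/10 = 50.0% | 18.7–81.3% |
| 5 | 1 | 50.0% | 5/9 = 55.6% | 21.2–86.3% |
| 5 | 2 | 50.0% | 5/8 = 62.5% | 24.5–91.5% |
| 5 | 3 | 50.0% | 5/7 = 71.4% | 29.0–96.3% |
| 3 | 0 | 3/10 = 30.0% | 3/10 = 30.0% | 6.7–65.2% |
| 3 | 1 | 30.0% | 3/9 = 33.3% | 7.5–70.1% |
| 3 | 2 | 30.0% | 3/8 = 37.5% | 8.5–75.5% |
| 3 | 3 | 30.0% | 3/7 = 42.9% | 9.9–81.6% |

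For R = 5 the excess over 50% is 5.6, 12.5 and 21.4 percentage points.

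**One would-be responder withdrawn before a response is documented**

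| R | Completers | All treated, counted as non-responder |
|---|---|---|
| 5 | 4/9 = 44.4% (13.7–78.8%) | 4/10 = 40.0% (12.2–73.8%) |
| 3 | 2/9 = 22.2% (2.8–60.0%) | 2/10 = 20.0% (2.5–55.6%) |

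Here the completer rate is too low, and the all-treated rule is lower still.

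**The case against.** The best counter-argument is that few failures would go unobserved. At Visit 4 (week 6), persisting carcinoids do not end treatment: YF476 continues, with an optional dose increase. At Visit 6 a patient without regression leaves only after the week-12 gastroscopy and biopsies, and can fairly be read as having completed the course. Lack of efficacy in Section 10.4 is one item in a general list, and no visit procedure acts on it before week 12. This stands as a limit on how often the problem would arise. It does not remove it, because 10.4 does permit earlier withdrawal on that ground. The protocol also never defines completing the study; if Visit 6 leavers were not completers, the distortion would be far larger. The point made here does not depend on that reading.

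Second, the statement that data collection stops is what patients are told about their own withdrawal, and may not govern withdrawal decided by the investigator. Data gathered beforehand, including a Visit 4 gastroscopy, remain, and Section 20.3 promises a full listing of CRF data, from which a reader could rebuild the denominator. That is fair, but a listing does not correct the rate reported as the primary result.

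Third, this is a descriptive pilot with no numerical success threshold, the intervals overlap widely, and every count above is assumed. Section 10.1 also words the cap as up to 10 completing, so the number treated could exceed 10. All of this bears on weight: nothing shows that a particular shift would change the decision to proceed.

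Fourth, counting withdrawals as failures is a convention and penalises an unrelated early withdrawal. The second table shows that cost.

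**Conclusion.** The concern holds. Within Section 18.1 the objective refers to all treated patients and the efficacy set to completers without major deviations, and Section 10.4 lets a treatment failure fall between the two.

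The direction depends on who leaves: upward if mainly non-responders are withdrawn, downward if mainly responders. With 10 treated and 5 responders, removing one to three non-responders adds about 6 to 21 percentage points; with 3 responders, about 3 to 13 points (33.3 − 30.0 to 42.9 − 30.0). With no exclusions the effect is nil. These figures rest wholly on assumed counts. The consequence is a possibly misleading point estimate in an exploratory trial, so the change is advisable rather than essential.

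**What to change.** Amend the Efficacy data text in Section 18.1 as follows:

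- The primary response rate is calculated among all patients who received YF476, the set that Section 18.1 already uses for safety.
- A patient withdrawn without a documented response counts as a non-responder. A response documented at the Visit 4 gastroscopy before withdrawal counts as a response.
- The set of completers without major deviations is kept as a supportive analysis.

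Sections 10.4 and 11.4 can stay as they are.

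The cost is one or two sentences, with no new visit, procedure or data. The reported rate may look less favourable, by 6 to 21 points in the assumed 5-of-10 cases with non-responders withdrawn. The rule is conservative when a patient leaves for an unrelated reason before a response is documented (40% against 44% among completers in the example); reporting the completer rate alongside makes that difference visible.

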#### 2.4 Type of trial

Single centre, open-label, pilot, phase 2, out-patient trial.

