#### 2.7 Methods

- Gastroscopy with photographs and video of carcinoids, and biopsies of antrum, corpus and carcinoids;
- Blood samples for assay of gastrin, CgA, and YF476, and serum for storage;
- Diary card: adverse events, concomitant medication and compliance; and
- Tolerability and safety assessments.

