#### Fourth, what should be the study design?

A placebo-controlled trial of a new type of therapy for gastric carcinoids such as YF476 would be the ideal study design. However, the proposed outcome measures are robust enough to assess efficacy in an open trial without a comparator.

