### Collection and processing of plasma for CgA assays:

4 mL venous blood will be collected into an EDTA tube and centrifuged at about 1500 G for 10 minutes at 4°C. The plasma will be transferred into 2 equal aliquots in polypropylene tubes, and stored at –70°C, before shipment to the HMR Analytical Laboratory, [name]. Plasma samples for CgA assay will be shipped once the patient has completed the study. All sample handling materials will be provided by the HMR Analytical Laboratory.

*Gastrin assay and plasma CgA assay:* Serum gastrin and plasma CgA will be measured by the HMR Analytical Laboratory using commercially available enzyme linked immunoassays (ELISA).

*Processing of blood samples for pharmacokinetic analysis:* YF476 is light-sensitive, so blood samples (4 mL) will be taken into foil-wrapped or amber lithium heparin tubes, and immediately placed on ice. Samples will be centrifuged at about 1500 G for 10 minutes at 4°C. Plasma will be transferred to foil-wrapped or amber polypropylene storage tubes. Plasma samples will be stored at –20°C within 90

minutes after collection, and stored in darkness until dispatch. Samples will be sent to Analytical Services, St George's Hospital, for analysis of YF476.

*Stored serum:* serum will be stored by the HMR Analytical Laboratory for assay of trial-related markers only, which will be decided upon at a later date.

*Gastroscopy:* a gastroenterologist who is experienced and trained in the procedure will do the gastroscopies and biopsies. Subjects must have fasted from food and fluids for at least 6 hours before the procedure. Before the procedure, patients will choose whether they want to be sedated with intravenous midazolam, or have their throat sprayed with a local anaesthetic. After gastroscopy, patients will rest until they are fully recovered from the procedure. They may eat 30 min after the procedure.

During the procedure, the distribution, number and size of any gastric carcinoids will be assessed visually, and the tumors will be photographed. A pair of standard biopsy forceps will be used as an internal standard for size correction between images. Biopsies will be taken of the antrum, corpus and carcinoids for histology assessment and assessment of ECL cell markers and biomarkers (such as CgA).

*Histologic evaluation:* [name], Liverpool, will do the histology. Histologic evaluation will include the following:

- haematoxylin and eosin (H&E) staining;

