# 20 Trial documentation

# 20.1 Protocol amendments

After the protocol has been approved by the main REC and the MHRA, no changes may be made without the agreement of both the investigator and the sponsor.

The MHRA and main REC do not need to approve any substantial change to the protocol that needs to be implemented urgently to avoid an immediate hazard to trial subjects. The sponsor will ensure that the MHRA and main REC are informed of urgent amendments in accordance with the detailed guidance to EU Directive 2001/20/EC and the standard operating procedures issued by NRES for NHS RECs.

All agreed protocol amendments will be recorded on a written agreement which will be signed and dated by the investigator and sponsor, and attached to the original protocol. The REC and/or MHRA must approve substantial amendments before they are implemented.

The following changes to the trial plan are permitted by this protocol, and will not be considered as amendments.

- (a) Additional visits, for example to monitor blood pressure, will be arranged if there is a potential risk of a drug-drug interaction (see Appendix 1).
- (b) Additional blood or urine samples may be taken for safety tests if required. The total volume of additional blood taken will not exceed 100 mL. Laboratory safety tests will be repeated, if the investigator has any safety concerns.
- (c) Up to 3 additional visits to the clinic will be permitted, in the event of a technical failure and/or it extra safety tests are needed.
- (d) Additional laboratory tests for ECL-cell markers, biomarkers and/or histology will be done on the gastric biopsies, if the results of other tests suggest that additional tests would be worthwhile.
- (e) Stored serum will be used for laboratory tests not yet defined but related to this trial only.
- (f) Visits 3 and 5 may be made up to 2 days before or after the scheduled day. Visits 4, 6 and 7 may be made up to 3 days before or after the scheduled day. Visits 9-12 may be up to 5 days before or after the scheduled day. Patients will be given sufficient YF476 to cover any delays. Therefore, up to 33 days extra YF476 may be taken by each patient, although every effort will be made to arrange patient's visits on the scheduled days.
- (g) It might not be possible to take a video of every gastroscopy. Photographs should suffice.

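### As the protocol stands, no blinded read decides the lesion size or lesion number route to primary response; extending the planned blinded read to every image set is a cheap improvement

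*Protocol*

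**What the plan says.** Section 2.4 describes a "Single centre, open-label, pilot, phase 2, out-patient trial". Section 7.9 accepts that a placebo-controlled trial would be ideal, and defends the open design on the ground that "the proposed outcome measures are robust enough to assess efficacy in an open trial without a comparator".

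Section 18.1 defines primary response by three routes joined by 'or'. Two are tumour routes, a "25% reduction in the size or number of endoscopically evident type I gastric carcinoids". The third is "a reduction of 25% in the gastric ECL cell density".

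The gastroscopy paragraph of section 14.14 says how the tumour data arise. During the procedure "the distribution, number and size of any gastric carcinoids will be assessed visually, and the tumors will be photographed", with biopsy forceps in view as a size reference between images. No blinding of the operator is mentioned. Sections 14.4 and 14.6 use the same visual inspection for the decisions at Visits 4 and 6.

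Section 18.1 then brings in a blinded endoscopist, unaware of history, dose and timing, who "will review a random sample of endoscopic images to report the size of endoscopic lesions". This appears under interobserver variability, and its only stated use is a kappa for agreement with the study endoscopist.

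On recording, section 2.7 lists "Gastroscopy with photographs and video of carcinoids", while section 20.1(g) allows that "It might not be possible to take a video of every gastroscopy. Photographs should suffice".

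**The concern.** Size and number are judged by someone who knows that the patient is on YF476, which visit it is and, in a single-centre trial, probably what was seen before. There is no control arm in which the same expectation would operate and cancel, so any tendency to see smaller or fewer lesions at follow-up goes into the response rate through these two routes. Section 18.2 lets the results decide whether the study stops or a larger trial follows, so the estimate has consequences even in a pilot.

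The protocol already has the means to limit this: a blinded endoscopist and photographs with a size reference. It uses them to describe agreement, and a kappa does not correct any patient's classification. Number gets no blinded read at all, although a fall in number alone is enough for response.

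**Working it through.** The protocol gives no figure behind this point, so there is none to reproduce. The main argument comes from setting the sections side by side. The arithmetic only illustrates scale.

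**1. Which read decides response?**
- Section 14.14: size and number are scored at the procedure, with no blinding stated.
- Section 18.1: the blinded read covers a sample, covers size only, and is used for kappa.
- No section says that the blinded read replaces, adjudicates or enters the response classification.

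It follows, by inference, that the on-site score drives the size and number routes.

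**2. Does blinded histology protect the endpoint?** Section 14.14 has all biopsy samples read by one blinded pathologist at the end of the study. Section 18.1 describes the blinded pathologist as reviewing a random sample, and the two should be reconciled. Even under section 14.14, histology protects only the ECL-density route. Because the routes are joined by 'or', a size or number call alone makes a responder.

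**3. How many patients would have a blinded pair?** A 25% change needs a baseline and a follow-up reading. Assume that whole examinations are drawn by simple random sampling, m out of M. The chance that a patient's baseline and one given follow-up are both drawn is m(m−1)/[M(M−1)]. Take M = 30 (10 patients × Visits 2, 4 and 6) or M = 40 (adding Visit 7).

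| Assumed fraction | M = 30 | Patients of 10 | M = 40 | Patients of 10 |
|---|---|---|---|---|
| 10% | 3·2/(30·29) = 0.007 | 0.07 | 4·3/(40·39) = 0.008 | 0.08 |
| 20% | 6·5/(30·29) = 0.034 | 0.34 | 8·7/(40·39) = 0.036 | 0.36 |
| 50% | 15·14/(30·29) = 0.241 | 2.4 | 20·19/(40·39) = 0.244 | 2.4 |
| 100% | 1 | 10 | 1 | 10 |

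Requiring one given follow-up is the strict case. If any follow-up will do, and draws are treated as independent with fraction f:
- Baseline plus Visit 4 or 6: f[1−(1−f)²] = 0.2 × 0.36 = 7% at f = 20%, and 0.5 × 0.75 = 37.5% at f = 50%.
- Adding Visit 7: f[1−(1−f)³] = 0.2 × 0.488 = 10%, and 0.5 × 0.875 = 44%.

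If complete patients were sampled, coverage would simply be f. For lesion number, blinded coverage is zero under every scheme, because the reader reports size only.

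**4. What could expectation do to the size route?** Assume log-normal reading error with coefficient of variation CV at each visit, no true change, and follow-up read a proportion b too small. Then P(observed fall ≥ 25%) = Φ{[ln 0.75 − ln(1−b)]/(s√2)}, with s² = ln(1+CV²). At CV = 15%, s√2 = 0.211:
- b = 0: Φ(−0.288/0.211) = Φ(−1.36) = 9%
- b = 10%: Φ((−0.288+0.105)/0.211) = Φ(−0.86) = 19%
- b = 15%: Φ((−0.288+0.163)/0.211) = Φ(−0.59) = 28%

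The same formula gives 2%, 10% and 19% at CV = 10%, and 15%, 26% and 33% at CV = 20%. The value at b = 0 is measurement noise that blinding would not remove. Only the excess over it, about 8 to 19 percentage points across these inputs, is what blinding addresses.

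**5. What is one patient worth?** 1/10 = 10 percentage points of response rate.

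**The case against.** **Pilot status.** Section 18.2 calls the trial exploratory, with up to 10 patients, no power calculation and a probably double-blind, placebo-controlled trial to follow. The open design is declared and there is no success threshold. This stands as to severity. It does not remove the point, since section 18.1 makes estimating the response rate the objective.

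**On-site scoring is inferred.** A reader might take the protocol to say that the unblinded score determines response. It never says so. The forceps reference suggests that some sizing from images is intended, by a reader not named, and section 18.1 defers to a SAP not seen here. This stands. What can be said is that the protocol assigns no blinded read to the task.

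**Broken pairs.** A reader might infer that sampling separates baseline from follow-up images. Section 18.1 gives neither sampling unit nor fraction, and sampling complete patients would fit its wording. This stands, so the coverage figures are conditional.

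**Assumed error inputs.** The reading CV and bias have no source in the documents. This stands.

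**Image counts may be worse than live counts.** Section 7.4 gives type I tumours as multiple and under 1 cm, and video is not guaranteed. Making an image count decisive could lose lesions seen live, perhaps unevenly by visit. This stands, and is why the fix treats size and number differently and leaves 20.1(g) alone.

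**Workload.** Forty sets omit gastroscopies in the extension (Visits 10 and 12, and optionally 8). That is correct, but the fix is confined to Visits 2 to 7.

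**Conclusion.** The point holds in a limited form. As written, the blinded endoscopist reads a sample, reports size but not number, and feeds only a kappa, so that read cannot confirm or correct each patient's tumour response. The size and number routes appear to rest on an unblinded visual assessment in a trial with no comparator, and blinded histology does not cover them.

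The missing blinded count and the kappa-only use can be read directly from section 18.1. That the on-site score decides response is a reasonable inference. The size of the effect is not known: pair coverage depends on an assumed sampling unit and fraction, and the misclassification rates on an assumed reading CV and bias. The documents do not support saying that the response rate is biased by a given amount, or that most patients will lack a blinded pair.

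For a pilot of up to 10 patients this is a worthwhile, cheap improvement, not a must-fix error.

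**What to change.** In section 18.1:

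1. Have the blinded endoscopist already planned read all Visit 2, 4, 6 and 7 image sets, so that every patient's set is complete. Present them in random order with visit and date removed, and have both size and number reported. The maximum is about 10 × 4 = 40 sets, and fewer where Visits 5 and 6 or Visit 7 are omitted.
2. State that this read decides the size route, using the forceps-calibrated images.
3. For number, report the response rate by the blinded count and by the on-site count, and state in advance which is primary, because photographs may miss lesions seen live.
4. State that the on-site read continues to guide patient management as now. Section 20.1(g) need not change.

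The kappa can stay, now based on all sets. The cost is a few hours of reading and some protocol and SAP wording, with no new reader and no new patient procedure. The downside is that image counts may be incomplete, which reporting both counts makes visible.
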